The number of patients per site, as included herein, is our goal and are, therefore estimates. If a site enrolls more patients than expected, the numbers to be enrolled at the alternate sites will be adjusted so that the final number of patients for each condition is not changed.

For the **severe** amblyopia study:

This is a pilot study on severe amblyopia. We adopt the same sample size as the calculation for moderate amblyopia, which is 28 for each group and a total of 56 patients.

4. Gender of the Subjects.

Male and female subjects are equally eligible to participate in this study.

5. Age Range of Adult Subjects.

Efficacy of Intermittent Occlusion Therapy Glasses for Amblyopia-Dense, Deprivation and Myopic Anisometropia

Amblyopia

Approved 02/08/16

Amended: 05/12/16; 06/27/16; 06/29/16; 07/26/16, 09/13/16, 09/19/16, 09/27/16, 12/15/16, 01/26/17, 03/02/17, 06/20/17, 11/1/17, 12/19/17, 08/27/18, 12/18/18

Not Applicable

6. Age Range of Pediatric Subjects. What is the age range of subjects who are children? What is the rationale for selecting this age range? If children are excluded, justification should be provided. *Note: Children should not be excluded from participating in clinical research unless there are justifiable scientific, ethical, or other reasons not to include them.*

The age range of pediatric subjects in this study is 3 to <8 years of age. Rationale for selecting age is to be consistent with the PEDIG Amblyopia studies. This age range is the most effective age for occlusion treatment.

7. Racial and Ethnic Origin.

There are no participant restrictions based on race or ethnic origin.

8. Inclusion Criteria. What are the specific inclusion criteria?

If patients are in the severe amblyopia category, the following criteria must be met for the patient to be enrolled in the study:

1. Age 3 to < 8 years
2. Amblyopia associated with strabismus (commitant or incommittant), anisometropia, or both
 - Criteria for strabismus: At least one of the following criteria must be met:
 - Heterotropia at distance and/or near fixation on examination (with or without spectacles)
 - History of strabismus surgery
 - Documented history of strabismus which is no longer present (which in the judgment of the investigator could have caused amblyopia)
 - Criteria for anisometropia: At least one of the following criteria must be met:
 - >0.50 D difference between eyes in spherical equivalent
 - >1.50 D difference between eyes in astigmatism in any meridian

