3. Visual acuity, measured in each eye without cycloplegia within 7 days prior to enrollment using the ATS single-surround HOTV letter protocol as follows:
 - Visual acuity in the amblyopic eye between 20/100 and 20/400 inclusive
 - Visual acuity in the sound eye 20/32 or better
4. Spectacle correction (if applicable) for measurement of enrollment visual acuity must meet the following criteria and be based on a cycloplegic refraction within 6 months:
 - Requirements for spectacle correction:
 - For patients meeting criteria for only strabismus (see 2.2 #2 above)
 - i. Hypermetropia if corrected must not be undercorrected by more than +1.50 D spherical equivalent, and the reduction in plus sphere must be symmetric in the two eyes. Otherwise, spectacle correction is at investigator discretion.
 - For patients meeting criteria for anisometropia or combined-mechanism (see 2.2 #2 above)
 - i. Spherical equivalent must be within 0.50 D of fully correcting the anisometropia
 - ii. Hypermetropia must not be undercorrected by more than +1.50 D spherical equivalent, and reduction in plus must be symmetric in the two eyes
 - iii. Cylinder power in both eyes must be within 0.50 D of fully correcting the astigmatism
 - iv. Cylinder axis in the spectacle lenses in both eyes must be within 6 degrees of the axis of the cycloplegic refraction
 - 5. Wearing optimal spectacle correction for a minimum of 4 weeks at the time of enrollment.
 - 6. Gestational age > 34 weeks and birth weight > 1500 grams
 - 7. Parent willing to accept randomization
 - 8. Parent willing to be contacted and has access to phone
 - 9. Parent does not anticipate relocation outside area of active study site

If patients are in the deprivation amblyopia category, the following criteria must be met for the patient to be enrolled in the study:

Efficacy of Intermittent Occlusion Therapy Glasses for Amblyopia-Dense, Deprivation and Myopic Anisometropia

Amblyopia

Approved 02/08/16

Amended: 05/12/16; 06/27/16; 06/29/16; 07/26/16, 09/13/16, 09/19/16, 09/27/16, 12/15/16, 01/26/17, 03/02/17, 06/20/17, 11/1/17, 12/19/17, 08/27/18, 12/18/18

- a) Age 3 to < 8 years
- b) Amblyopia due to previous congenital or developmental cataract surgery.
- c) Visual acuity, measured in each eye without cycloplegia within 7 days prior to enrollment using the ATS single-surround HOTV letter protocol as follows:
 - a. Visual acuity in the amblyopic eye between 20/40 and 20/400 inclusive

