Clinical Testing before randomization

Examination procedures include:

1. Visual Acuity within 7 days of enrollment

Measurement of visual acuity in each eye (weaker eye first) by the ATS single-surround HOTV testing protocol throughout the whole study. Aspects of the testing protocol that are specific to this study are:

- Visual acuity of the amblyopic eye must be tested without cycloplegia.
- Patients currently wearing spectacles must have enrollment acuity measured while wearing spectacles - trial frames or phoropter cannot be used.

2. Ocular motility examination within 7 days

Measurement of alignment by Simultaneous Prism and Cover Test (SPCT) in primary position at distance and near

3. Ocular Examination within 6 months

Complete ocular examination, including dilated fundus examination, to rule out a cause for reduced visual acuity other than amblyopia.

4. Titmus fly and Randot Preschool Stereoacuity test within 7 days

5. Cycloplegic Refraction within 6 months

Cycloplegic refraction using cyclopentolate 1%

Randomization

Randomization will use a computer-generated number with block design. Each patient with **severe** amblyopia will be randomly assigned to one of two groups:

- IO-therapy glasses treatment group: 12-hour daily IO-therapy glasses (total occlusion time: 6 hours)
- Standard patching control group: 6-hour daily patching (total occlusion time: 6 hours)

Each patient with **deprivation** amblyopia will receive IO-therapy glasses.

According to visual acuity, they will receive one of two IO-therapy glasses treatment regimen: 1) If the amblyopic eye is between 20/40 to 20/80 inclusive, 4-hour IO-therapy glasses, or 2) If the amblyopic eye is between 20/100 to 20/400 inclusive, the child will receive 12-hour IO-therapy glasses.

All patients in the myopic anisometropic amblyopia group will be enrolled in the Amblyz™ group. The treatment regimen will be dependent on the visual acuity of the amblyopic eye and the eye doctor's recommendation for treatment hours. The eye doctor will follow the NIH PEDIG study suggestions: 4 hours/day of wear for moderate amblyopia and 12 hours/day wear for severe amblyopia).

For the IO-therapy glasses treatment group, the glasses will have a TheraMon® microsensor attached.⁵

For both the IO-therapy group and the patching control group:

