- Treatment is continued until there is no further improvement in amblyopic eye acuity (improvement defined as >1 line) between two consecutive 12-week visits, confirmed by a re-test. Once there is no improvement of one or more lines, the patient's participation in the study is over and treatment is at investigator's discretion.

Notes

1. The study will provide patches or IO-therapy glasses.
2. If a patient is noncompliant with treatment, the parents should be encouraged to persist with their efforts to treat to the best of their ability.
3. Prior to deviating from the treatment protocols or prescribing non-protocol treatment, the situation should be discussed with the PI.

Efficacy of Intermittent Occlusion Therapy Glasses for Amblyopia-Dense, Deprivation and Myopic Anisometropia

Amblyopia

Approved 02/08/16

Amended: 05/12/16; 06/27/16; 06/29/16; 07/26/16, 09/13/16, 09/19/16, 09/27/16, 12/15/16, 01/26/17, 03/02/17, 06/20/17, 11/1/17, 12/19/17, 08/27/18, 12/18/18

Randomization of Eligible Patients

1. Once a patient is randomized, the patient will be included in the analysis regardless of whether the assigned treatment is received or not. That is to adhere to “intent-to-treat” design. Thus, the investigator must not randomize a patient until he/she is convinced that the parent/guardian will accept and comply with either of the treatment regimens. Regardless of whether the patient receives the assigned treatment or not, the patient is still considered enrolled in the study and every effort should be made to perform the follow-up examinations according to the study protocol.
2. A patient is officially enrolled when the randomization process is completed.

Delay in Randomization

1. Visual acuity testing and the ocular motility examination must be performed no more than 7 days prior to randomization. If randomization is delayed beyond 7 days, then these tests must be repeated to confirm eligibility and establish the baseline measures for the study.
2. No other parts of the examination (including the refraction) need to be repeated if they were performed within 6 months prior to randomization.

Compliance

A calendar log will be maintained by all families. These logs will be reviewed at each of the protocol visits. The investigator's assessment of compliance will be recorded on the Follow-up Examination Form.

Follow-up Interactions

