After randomization, all patients (from both severe amblyopia and deprivation amblyopia groups) will have the following study visits/interactions:

Telephone Call

- Each patient will be contacted by the coordinator via telephone 4 weeks following the beginning of treatment to answer any questions and to encourage compliance with treatment.
- 12 ± 1 weeks after treatment begins : primary outcome visit

Primary Outcome Visit (occurs 12 ± 1 weeks after treatment begins)

Testing will include the following:

1. Visual acuity

Measured in each eye (worse eye first) by a certified examiner using the ATS single-surround HOTV acuity protocol.

2. Titmus fly and Randot Preschool Stereoacuity test

3. Ocular alignment assessed with the SPCT

4. Re-testing of visual acuity in the amblyopic eye (if indicated)

If amblyopic eye visual acuity has not improved from randomization by at least one line, then the acuity will be re-tested at this visit.

The results of the re-test will be used only to determine if the patient will continue study participation with the same study-mandated treatment. The first visual acuity will be used as the primary outcome visual acuity. If neither the test nor the re-test is one line better than the visual acuity at treatment, then study participation ends.

Efficacy of Intermittent Occlusion Therapy Glasses for Amblyopia-Dense, Deprivation and Myopic Anisometropia

Amblyopia

Approved 02/08/16

Amended: 05/12/16; 06/27/16; 06/29/16; 07/26/16, 09/13/16, 09/19/16, 09/27/16, 12/15/16, 01/26/17, 03/02/17, 06/20/17, 11/1/17, 12/19/17, 08/27/18, 12/18/18

Follow-Up Visits after the Primary Outcome Visit

For patients in either treatment group with at least one line of improvement in amblyopic eye acuity at the primary outcome examination, follow-up visits will occur every 12 ± 1 weeks until no improvement of one or more lines is seen.

At each post-primary outcome visit, visual acuity will be measured in each eye (worse eye first) by a certified examiner using the ATS single-surround HOTV acuity protocol. Acuity in the amblyopic eye will be re-tested during the visit if visual acuity has not improved from the last visit by at least one line.

Future treatment plans depend on each visual outcome in the amblyopic eye:

- If the patient's vision in the amblyopic eye is improved 1-2 lines, continue the study for another 12 weeks;
- If no improvement for one visit, continue the study for another 12 weeks;
- If no improvement for two visits, stop.

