Study participation will end only after a post-primary outcome visit at which amblyopic eye acuity shows no improvement of one or more lines on both an initial test and on a confirmatory re-test.

For all follow-up visits:

- Compliance will be evaluated with calendar log and microsensor.
- For patients who wear glasses with microsensors attached, data will be logged by connecting the microsensors to the reading station via antenna at 2-3 cm distance from the antenna. A USB cable transfers the data to a PC for storage; wearing times will be evaluated using the TheraMon® Software and compared to the wearing times protocol. Data will be recorded on the Follow-up Examination Form.

Test	Visit / Interaction			
	Enrollment	4 wk phone call	Primary Outcome 12 ± 1 wk (by masked examiner)	Every 12 ± 1 wks after primary outcome** (by masked examiner)
Telephone call		X		
Distance acuity each eye*	X		X	X
Ocular alignment	X		X	X
Titmus Fly	X		X	
Randot Preschool Test	X		X	
ATS questionnaire			X	X

* Using ATS single-surround HOTV acuity testing protocol on study certified vision tester.

** For patients whose amblyopic eye acuity has improved by ≥ 1 line at the 12-week visit, visits occur every 12 ± 1 weeks until no improvement of one or more lines.

Additional visits can be performed at the discretion of the investigator. A Follow-up Examination Form should be completed for every exam (not just the minimum required exams).

Extension Studies after Primary Outcome

Efficacy of Intermittent Occlusion Therapy Glasses for Amblyopia-Dense, Deprivation and Myopic Anisometropia

Amblyopia

Approved 02/08/16

Amended: 05/12/16; 06/27/16; 06/29/16; 07/26/16, 09/13/16, 09/19/16, 09/27/16, 12/15/16, 01/26/17, 03/02/17, 06/20/17, 11/1/17, 12/19/17, 08/27/18, 12/18/18

For patients who are randomized in the control patching group, after primary outcome at 12 weeks, if the patients desire to use IO-therapy glasses for treatment, they can use IO-therapy glasses for treatment as an extension study. This will not apply for those patients with deprivation amblyopia.

Stereoacuity

Differences between treatment groups in stereoacuity at the 12-week outcome will be assessed using a comparison of the distributions with the exact Wilcoxon rank sum test.

Primary Analysis for Safety

Sound Eye Acuity Data

The loss of 2 or more lines in sound eye visual acuity from baseline to the 12-week masked exam will be tabulated for each treatment group.

Ocular Alignment

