Ocular alignment will be assessed at baseline and at 12 weeks after randomization. Development of new strabismus (no tropia at baseline and the presence of near and/or distance tropia at follow-up) or an increase from baseline ≥ 10 PD will be tabulated by treatment group. Similarly, disappearance of a heterotropia and a decrease in the angle of a preexisting strabismus by ≥ 10 PD will be tabulated.

Sample Size:

The sample size for this study was calculated based on a standard two-sided trial with a continuous outcome. The calculations assume 5% type I error with 80% power; the standard deviation of change from the baseline was 0.14, and the effective size difference was 0.12. Therefore, we anticipate that we will require 46 total subjects (i.e., 23 for each group).⁴ Because the IO therapy glasses are a novel device used to treat severe amblyopia, we are uncertain how many 3-8 year-old patients will drop out from the study. According to an average 15% dropout rate in previous amblyopia studies^{1, 6}, we overestimate the sample size to be 28 in each group to account for attrition.

12. **Drugs and Devices.** Does this study involve investigational drugs or devices (test articles) and/or FDA approved drugs/devices used for off-label purposes? If the study involves a test article, identify the drug/device, provide the IND or IDE number and identify the holder of the number. If the study involves drugs/devices used for off-label purposes, this should be stated. If the study does not involve any test articles or drugs/devices used for off-label purposes, this should be stated. *Note: Research involving investigational drugs must comply with the FDA IND Regulations (21 CFR 312) govern research with medical devices. The FDA IDE Regulations (21 CFR 812) govern research with medical devices. In some cases it may be in the best interest of the subject and the investigator for an IND/IDE to be submitted to FDA even when there is no legal requirement.*

Yes. We use IO-therapy glasses and thermosensor. We attach the medical device form of IO-therapy glasses and thermosensor. IO-therapy glasses are FDA approved.

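### The stereoacuity comparison at 12 weeks ignores the baseline stereoacuity that is already measured; a rank test with two baseline strata would be a cheap gain in precision

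*Combined protocol and SAP*

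**What the plan says.** All references are to the combined protocol and SAP, item 11 unless stated.

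- **Stereoacuity.** Differences between the two randomised groups "at the 12-week outcome will be assessed using a comparison of the distributions with the exact Wilcoxon rank sum test". No baseline term, stratum or change from baseline is mentioned, and the text does not say which stereo test supplies the outcome.
- **Clinical Testing before randomization, item 4.** Baseline is measured: "Titmus fly and Randot Preschool Stereoacuity test within 7 days". The visit table lists both stereo tests at enrolment and at the primary outcome visit.
- **Delay in Randomization.** Item 1 requires only acuity and motility to be repeated after 7 days. Item 2 adds: "No other parts of the examination (including the refraction) need to be repeated if they were performed within 6 months prior to randomization".
- **Randomization.** "Randomization will use a computer-generated number with block design". No stratification factor is given here or in item 3.
- **Status of the outcome.** Under Primary Outcome Visit, acuity is primary: "The first visual acuity will be used as the primary outcome visual acuity". Item 3 calls the severe-amblyopia study a pilot and says "We adopt the same sample size as the calculation for moderate amblyopia".
- **Other outcomes.** Sound-eye acuity loss and alignment changes are tabulated only. The supplied text names no test or model for 12-week amblyopic-eye acuity.

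**The concern.** Some children with severe amblyopia may start with no measurable stereopsis and others with some. If the starting level predicts the 12-week level, a test that ignores it treats that predictable variation as noise and loses power. With 23 to 28 children per arm, the arms may also differ by chance in how many start at nil. Neither the described randomisation nor the stated test deals with such a difference, and a reader who saw one would have no prespecified adjusted result to turn to.

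Two gaps in specification bear on any remedy. The choice between Titmus fly and Randot Preschool is left open. The allowed age of the baseline value is also unsettled, because one section asks for testing within 7 days and another does not require it to be repeated after a delay.

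**Working it through.** **1. The plan's own figure.** The Sample Size paragraph says "the standard deviation of change from the baseline was 0.14, and the effective size difference was 0.12", with 5% two-sided error and 80% power. The standardised difference is 0.12/0.14 = 0.857. A two-sample t-test then needs 22.37, so 23 per group (81% power at 23). Allowing 15% dropout, 23/0.85 = 27.06, which rounds up to 28. Both stated numbers reproduce. They concern a continuous change from baseline; no power or sample size is stated for stereoacuity.

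**2. The two tests compared.** Let W_s be the rank sum of the IO-therapy arm within baseline stratum s, and n_s the number of children in it. The van Elteren statistic is T = Σ_s [W_s − E(W_s)]/(n_s + 1), with its null distribution found by permuting arm labels within strata. With a single stratum it is the planned Wilcoxon test.

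**3. Assumed inputs.** The documents give no stereoacuity levels, nil share, effect or correlation. Main simulation: latent bivariate normal with correlation ρ between baseline and 12 weeks; six levels, the lowest being nil; nil share 50%, 80% or 90%; latent shift 0.7 SD; 23 per arm; two strata (nil versus measurable); permutation versions of both tests (999 permutations); 10,000 trials per setting.

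Power, unadjusted / stratified (change in points):

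| ρ | 50% nil | 80% nil | 90% nil |
|---|---|---|---|
| 0 | 56.7 / 55.3 (−1.4) | 44.8 / 44.0 (−0.8) | 30.6 / 31.0 (+0.4) |
| 0.3 | 56.8 / 58.0 (+1.2) | 45.5 / 46.1 (+0.6) | 30.6 / 31.1 (+0.5) |
| 0.5 | 56.0 / 60.9 (+4.9) | 44.6 / 48.0 (+3.4) | 31.3 / 33.7 (+2.4) |
| 0.7 | 57.1 / 70.9 (+13.8) | 43.6 / 53.3 (+9.7) | 30.7 / 36.4 (+5.7) |

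**4. Second set of assumptions.** Shift 0.857 (borrowed from the Sample Size paragraph, which is not about stereoacuity), nil share 30 to 85%, four to seven levels, 23 and 28 per arm, normal approximation. With two strata the change is about −1 to −1.5 points at ρ = 0, −0.3 to +0.9 at 0.3, +1.9 to +5.0 at 0.5 and +8 to +11 at 0.7. Permutation checks at 23 per arm gave −0.7 and +0.5 at ρ = 0, and +6.6 and +4.1 at ρ = 0.5 (simulation SE 0.4 to 0.7). One further run had a worst loss of 2.0 points at ρ = 0 (simulation error about 0.5 to 0.8).

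**5. Finer strata.** At ρ = 0, three strata lose 1.8 to 3.3 points. One stratum per stereo level loses 2.9 to 9.9 points at ρ = 0 and still 1.5 to 6.6 at ρ = 0.3. With 46 to 56 children, small strata leave few within-stratum comparisons.

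**6. Type I error.** Averaged over all null trials at 50% and 80% nil, rejection is 4.0 to 4.8% unadjusted and 4.4 to 5.1% stratified. An imbalance of 5 or more nil children occurs in 17 to 19% of trials at 50% nil, 9 to 10% at 80% and about 3% at 90%. Given that imbalance, the unadjusted test rejects:

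| ρ | 50% nil | 80% nil |
|---|---|---|
| 0 | 4.1% | 3.9% |
| 0.3 | 6.0% | 4.8% |
| 0.5 | 8.2% | 8.4% |
| 0.7 | 10.7% | 12.4% |

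The stratified test stays at 4.7 to 5.2% in the ρ = 0.5 and 0.7 cells.

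**The case against.** The strongest reply is that nothing here is wrong. An exact rank test in a randomised comparison holds its error rate, the outcome is not primary, the study is described as a pilot, and no power is claimed for stereoacuity. All benefits rest on assumed distributions and largely vanish at correlation 0.3 or below. This stands, and it sets the weight of the point. It does not remove it, since the measurements are already collected and the expected cost is small.

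Four stronger readings are tempting, and the documents do not support them.

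- **That the stated test is biased or invalid.** It is not; its overall error is nominal or slightly below.
- **That chance imbalance generally inflates error.** Inflation is conditional on an unlucky allocation and becomes clear only at a correlation of about 0.5 or more.
- **That stratifying is nearly free however it is done.** That holds for two strata only.
- **That the acuity analysis is also unadjusted.** A standard deviation of change in the sample-size paragraph is a planning input, not a stated analysis. The cover page also lists a statistical analysis component, so silence in the supplied text is weak evidence. No power comparison for acuity is warranted.

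A fair further objection is that stratifying could lose children with no baseline stereo result, although the plan keeps every randomised child in the analysis. The fix must therefore include a rule for them.

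**Conclusion.** The point holds as an inexpensive improvement in precision, worth making but not a correction of an error. With two strata and 23 per arm, the change in power is about −1 to −2 points at correlation 0, about nil at 0.3, about +2 to +5 at 0.5 and about +8 to +14 at 0.7. At 90% nil the gain at 0.7 falls to about 6 points. These figures depend on the assumed levels, nil share, shift and correlation, none of which the documents supply; an older baseline value would tend to lower the correlation and so the gain. Confidence is high on what the plan states and on the direction of the result, and moderate on its size. The unnamed stereo test and the unsettled age of the baseline value need resolving whatever the correlation.

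**What to change.** Amend the Stereoacuity paragraph as follows.

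1. Make the main comparison a van Elteren (stratified Wilcoxon) test, exact by permutation within strata, with exactly two baseline strata: nil versus measurable stereopsis. Do not use finer strata.
2. Keep the unadjusted exact Wilcoxon test as a sensitivity analysis.
3. Name in advance which test, Titmus fly or Randot Preschool, supplies both the outcome and the stratum.
4. Use the last value before randomisation and state its allowed age, reconciling Clinical Testing before randomization with Delay in Randomization.
5. Fix in advance the stratum for children with no obtainable baseline result (for example, with nil), so that none is dropped for that reason.

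The cost is a few sentences, with no extra visits or children, plus the 1 to 2 power points lost if baseline proves uninformative. An older pre-randomisation value is still a valid stratum. Only if the sponsor wants it within 7 days for every child must stereo testing join the tests repeated after a delay.

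When the acuity analysis is written, ANCOVA of 12-week logMAR on arm and baseline logMAR is worth considering; that is a suggestion, not part of this finding.

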If skin irritation occurs, the parent will be advised to put an emollient on the skin and discontinue use of the patch for a day. Patching could potentially decrease the visual acuity in the sound eye, although this is almost always reversible. However, this occurrence is extremely unlikely since the sound eye will have several hours without occlusion each day. The diagnosis and management of reverse amblyopia is left to the investigator's judgment. Patching could precipitate the development of an ocular deviation (strabismus), although this has been found to be very rare in previous studies and indistinguishable from the natural history of strabismus. If treatment precipitates the development of an ocular deviation (e.g., esotropia in child with hyperopia), the parent will be advised to have the patient see the investigator as soon as possible.

Risks of IO-therapy glasses

The children adjust to the flickering of the lens of the strong eye easily. At the beginning, IO-therapy glasses may induce a transient headache or some discomfort.

However, just like traditional patching, IO-therapy glasses could potentially decrease the visual acuity in the sound eye, although this is almost always reversible. However, this occurrence is extremely unlikely since the sound eye will have several hours without occlusion each day and the risk is the same with either the IO-therapy glasses or traditional patching. The diagnosis and management of reverse amblyopia is left to the investigator's judgment. So far, there is no significant decrease (≥ 2 lines logMAR) in the visual acuity in the sound eye reported.⁴

As with traditional patching treatment, IO-therapy glasses could precipitate the development of an ocular deviation (strabismus), although this has been found to be very rare in previous studies and indistinguishable from the natural history of strabismus. If treatment precipitates the development of an ocular deviation (e.g., esotropia in child with hyperopia), the parent will be advised to have the patient see the investigator as soon as possible.

Risks of microsensor

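### A harm recorded before week 12 that resolves, or occurs in a child with no 12-week exam, goes uncounted in the sound-eye table and, on its natural reading, the alignment table

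*Combined protocol and SAP*

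**What the plan says.** All places are in the combined protocol and SAP.

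- **Sound eye.** Section 11, Primary Analysis for Safety, Sound Eye Acuity Data, tabulates by group "The loss of 2 or more lines in sound eye visual acuity from baseline to the 12-week masked exam".
- **Alignment.** Section 11, Ocular Alignment, opens with "Ocular alignment will be assessed at baseline and at 12 weeks after randomization". It then tabulates an increase of 10 PD or more, or new strabismus, defined as "no tropia at baseline and the presence of near and/or distance tropia at follow-up".
- **Exams before week 12.** Under Follow-up Interactions, the only scheduled contact between enrolment and the 12-week visit is a telephone call at 4 weeks. The notes below the visit table add: "Additional visits can be performed at the discretion of the investigator. A Follow-up Examination Form should be completed for every exam".
- **Expected course of harm.** Section 14 says that "IO-therapy glasses could potentially decrease the visual acuity in the sound eye, although this is almost always reversible", and says the same of patching. For a deviation that develops on treatment, "the parent will be advised to have the patient see the investigator as soon as possible".
- **Attrition.** Section 11, Sample Size, raises 23 per group to 28: "According to an average 15% dropout rate in previous amblyopia studies".

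The available text sets out no adverse-event collection or analysis, and no rule for a child without a 12-week exam. Section 16 assigns safety monitoring to the university's IRB.

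**The concern.** The protocol foresees that some harms may be seen early, at visits outside the schedule, and requires those exams to be recorded. The sound-eye table then looks only at status at week 12. If the harm has gone by then, the child is tabulated as event-free. If there is no 12-week exam, the child cannot be counted as having had an event. The alignment table works the same way if its follow-up means the 12-week assessment named in the sentence before it.

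At stake is the safety message. Section 14 states that the risk to the sound eye is equal under glasses and patching, and the Sample Size paragraph describes the glasses as novel for severe amblyopia. This trial's tables are where readers would look for evidence on that statement. As written, they could show no event while one is on a completed form.

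**Working it through.** **1. The plan's own figure.** The inputs from section 11, Sample Size, are SD 0.14, difference 0.12, two-sided 5% error and 80% power.

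- Normal approximation: n per group = 2 × (1.960 + 0.842)² × 0.14² / 0.12² = 21.4, so 22.
- Two-sample t version: 22.37, so 23, which matches the plan.
- Dropout: 23 / (1 − 0.15) = 27.1, so 28, which also matches.

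The sample size is not in dispute. It supplies the numbers of children used below.

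**2. Where a recorded harm would appear.** The safety definitions, the note on extra exams and section 14 together give:

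| Course of the harm | Sound-eye table | Alignment table (natural reading) |
|---|---|---|
| Present at the 12-week exam | Event | Event |
| Recorded at an extra exam, resolved by week 12 | No event | No event |
| Recorded at an extra exam, no 12-week exam | Cannot be counted | Cannot be counted |

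In the last two rows the finding stays on the Follow-up Examination Form, and the available text gives it no other route into the results. The sound-eye column follows from explicit wording. The alignment column depends on what 'at follow-up' means.

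**3. Children without a 12-week exam.** At the planned dropout, 28 × 0.15 = 4.2 per arm have no 12-week exam and 28 − 4.2 = 23.8 do. Over both arms, 56 × 0.15 = 8.4.

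**4. Scale under assumed rates.** The documents give no event rate. For an assumed risk p per child, the chance of at least one event among 8 such children is 1 − (1 − p)⁸:

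- p = 2%: 15%
- p = 5%: 34%
- p = 10%: 57%

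These figures take events as independent and dropouts as having the stated risk. Only events actually recorded at an extra exam could be recovered, so the recoverable share is smaller. Events that resolve before week 12 in children who complete are additional, and the documents give nothing from which to estimate them.

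**5. What one or two events mean here.** Suppose about 24 children in an arm are examined at week 12 and none has an event. The exact two-sided 95% upper limit is 1 − 0.025^(1/24) = 14.2%, so a zero is weak evidence already. One or two events on file but outside the table would be 1/28 = 3.6% or 2/28 = 7.1% of the arm. Both denominators are assumptions, since the plan states none.

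**The case against.** A masked exam at one fixed time, the same in both arms, is a sound basis for a safety table in what the protocol calls a pilot. Extra exams are discretionary. Nothing says that they include the study acuity and alignment tests or a masked examiner, and the arm examined more often has more chances to cross a threshold. That stands, and it is why the 12-week tables should remain primary. It does not justify leaving recorded harms out of the report.

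Several stronger readings are tempting but not supported:

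- *Both tables certainly exclude early findings.* This is explicit only for the sound eye. For alignment, 'at follow-up' could be read to cover any exam with a Follow-up Examination Form, although the preceding sentence points to week 12.
- *Early harm data will exist.* They may. The advice to return early concerns deviation, not sound-eye acuity. Section 14 gives no time frame for recovery, considers sound-eye loss very unlikely, and says that no loss of 2 or more lines had been reported with the glasses.
- *Children harmed by treatment will drop out.* Section 11, Randomization of Eligible Patients, keeps a child enrolled, with follow-up exams sought, whether or not the assigned treatment is received. The 15% is a planning figure with no stated link to harm. That rule does not, however, supply a missing 12-week exam or bring a harm recorded before week 12 into the tables.
- *The comparison is biased towards no difference.* That would require early harm, or its detection, to differ by arm in a particular way. The plan sets out only tabulation, with no between-arm safety test.
- *The rate is understated by a known percentage.* Any such figure comes from an assumed split of a few events and an assumed denominator.

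**Conclusion.** The point holds as a gap in the tabulation rule, not in data capture. A harm recorded at an extra exam before week 12 is not counted in the sound-eye table if it has resolved by week 12 or if the child has no 12-week exam. The same applies to the alignment table on its natural reading.

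The size is unknown. What the documents support is that about 4 of 28 children per arm would have no 12-week exam at the planned dropout, and that with so few children one or two omitted events could change the safety message. The direction of any between-arm distortion depends on whether early harm and extra exams differ by arm.

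The conclusion assumes that the text withheld from review contains no further safety analysis. It concerns safety reporting only and leaves the primary efficacy result untouched. It should be settled before the data are analysed.

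**What to change.** In section 11, Primary Analysis for Safety:

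1. Keep the masked 12-week tables as primary, and state that 'at follow-up' in the alignment definition means the 12-week exam.
2. Add one descriptive table by randomised arm. Count children with a recorded sound-eye loss of 2 or more lines, or with a new tropia or an increase of 10 PD or more, at any exam from randomisation through the 12-week visit.
3. Give the counts out of all randomised children. A denominator restricted to examined children would depend on the outcome, because suspected harm may prompt the exam.
4. Beside the counts, show for each arm the number of children with any post-baseline exam, the number without a 12-week exam and the number of extra exams. For each event, state whether it had resolved by week 12.

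The cost is a few sentences in the plan and one table from forms already required, with no added visits. The downside is that extra exams may be unmasked and unequal between arms, so the added counts are descriptive and do not support a formal comparison. No change to clinical management is proposed.
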